"Inpatient Diabetes Mellitus (DM) Management With Continuous Glucose Monitoring Devices, a Pilot Study."

NCT Number: NCT02904512

Uploaded 10/25/2018

A. Background and Significance:

Several observational studies have shown that uncontrolled hyperglycemia in hospitalized patients in the non-critical care, non-Intensive Care Unit (non-ICU) setting is associated with prolonged length of stay, increased mortality and an increased incidence of infections [1-6]. Randomized clinical trials in both the critical and the non-ICU settings have shown that by improving glucose control there is a decrease in the incidence of infections, length of stay and inpatient health care costs [7-10].

While hyperglycemia has known deleterious effects, profound hypoglycemia can cause neurological damage [11], as well as induce fatal arrhythmias, due to increased counter regulatory hormones, such as catecholamines, especially in patients with preexisting coronary artery disease [12, 13]. Hypoglycemia in the inpatient setting is more common than in the outpatient setting, with prevalence rates among medical and surgical patients ranging between 3-30% [7, 14-17]. Hypoglycemic events in the hospital setting have been associated with increased mortality and prolonged length of stay [18].

Almost all patients with DM (Diabetes Mellitus) monitor their glucose values with Point of Care (POC) blood glucose testing. The accuracy of most handled glucose meters is at the very least "not optimal" and the FDA allows a variance of 20% for meter measurements and 10% for central laboratory measurements as compared to the true blood glucose levels [19]. Continuous glucose monitoring (CGM) systems have evolved as useful devices providing excellent clinical care in patients with DM [19]. These systems detect glucose in subcutaneous interstitial fluid using a glucose sensor that transmits glucose measurements to a receiving device that reads out average glucose levels every 5 minutes. Using traditional glucose monitors, gaps occur during which time glucose excursions are undetected/ undocumented. CGM provides glucose measures during these time gaps. CGM devices have been shown to improve glycemic control and decrease duration of hypoglycemia in outpatients with DM. CGM are recommended in patients with DM (outpatient setting) with hypoglycemic unawareness, as a declining glucose trend can trigger hypoglycemia-threshold alarms to alert the patient prior to the onset of severe hypoglycemia [20].

Several published studies have examined the use of CGMs in the inpatient setting [21-30]. Most of the studies have been performed in the ICU setting [21-28], where CGM use may not be beneficial to the patients, as patients are monitored closely, with glucose values checked every 1 hour or even more frequently. In the non-ICU setting, where the majority of patients are hospitalized (General Wards), the data for using CGM are limited. In a single arm observational study Burt and colleagues showed that CGM was able to detect for hyperglycemia excursions and more hypoglycemia events than POC-FSBG [29]. In a study that examined the use of CGM in hospitalized patients with DM2 [30], CGM use was able to detect more hypoglycemic events (55 vs 12, p=0.0001) compared to the group that was managed with POC-FSBG. 26.3% of the hypoglycemic events were asymptomatic and the majority of these events were identified by CGM use (86.7%). CGM use was more likely to detect nocturnal and daytime hypoglycemic events (p=0.0399 and 0.0066 respectively). Notably participants in this clinical trial [30] were insulin naïve (not previously on insulin) DM2 subjects, a group of patients that may not be at high risk for hypoglycemia. Both of these studies [29, 30] showed that CGM use can detect more hypoglycemic events. However, as these studies were blinded for both investigators and patients, interventions to prevent hypoglycemia were not performed. The next reasonable step is to examine whether CGM use can prevent hypoglycemic events.

In this pilot study we propose to examine the clinical use of CGM in hospitalized insulin treated patients with DM2, admitted in General Medicine Wards setting who are at higher risk for hypoglycemia. We anticipate that our intervention will decrease the number of hypoglycemic events, which represents a significant safety concern in the inpatient setting. We also anticipate that our intervention may decrease hyperglycemia (mild or severe) and therefore may improve clinical outcomes such as nosocomial complications and length of stay. This pilot study may lead us to obtain preliminary data that will help us to design larger clinical studies

B. Aims:

In this randomized clinical trial, we will evaluate whether inpatient use of CGM devices are beneficial in subjects with DM2 in the non-critical care setting (general wards).

Groups:

Half of the hospitalized patients will be monitored with POC testing and non blinded CGM (for both the investigators and the subjects, **Intervention Group**). Management of this group of patients will be based on glucose values obtained by CGM and POC testing.

Half of the subjects will be monitored by POC testing only. CGM results will be blinded (for both the investigators and the subjects, **Control Group**). Management of this group of patients will be based on glucose values obtained by POC-FSBG only.

Aim 1: To determine if we can prevent more hypoglycemic values/ events in the Intervention Group vs Control group.

Hypothesis 1: CGM use (un-blinded) and POC-FSBG will prevent more hypoglycemic values/events compared to subjects that we will be managed by POC-FSBG only.

Aim 2: To determine if subjects that are in the Intervention Group will have decreased hyperglycemia compared to control Group.

Hypothesis 2: Subjects that will be managed by CGM and POC-FSBG will have decreased hyperglycemia compared to subjects that will be managed by POC-FSBG only.

Aim 3: To determine if subjects that are in the Intervention Group will have decreased severe hyperglycemia compared to control Group.

Hypothesis 3: Subjects that will be managed by CGM and POC-FSBG will have decreased severe hyperglycemia compared to subjects that will be managed by POC-FSBG only.

C. Design and Methods:

Human Subjects

Inclusion criteria: \geq 21 years of age; history of type 2 DM managed with insulin (either basal bolus, basal with per os DM medications) who also fulfill 1 or more of the following criteria, all known risk factors of hypoglycemia [31-34]: Insulin use of more than 0.6 u/kg, age \geq 65, BMI \leq 27, renal failure, liver failure, active malignancy, congestive heart failure, CVA or sepsis. We will also include hospitalized individuals with type 2 DM treated with insulin that developed a significant hypoglycemic episode in a recent (<6 months) hospitalization.

Exclusion criteria: Subjects that have a history of type 1 DM. History of type 2 DM that are being treated with diet or any combination of oral antidiabetic drugs only, as these patients are less likely to benefit from CGM use. We will also exclude subjects that have significant hyperglycemia or DKA that requires treatment with intravenous insulin infusion and any patients that need hospitalization in the critical care (ICU) setting. Pregnant patients, patients receiving glucorticoids in doses (equivalent) to \geq 20 mg of hydrocortisone/day, or patients that are expected to require a hospital stay <3 days will also be excluded [35]. Finally, we will exclude any individual with a mental condition rendering the subject incapable of understanding the objectives and potential consequences of the study.

The ethics committee of the University of Maryland and VABMC will approve the study protocol. Informed consent will be obtained from all enrolled subjects.

Lab Values and Glucose Measurements:

All participants will have an Hba1c, CBC and BMP at the time of enrollment in the study, lab values that represent standard of care in admitted subjects with DM.

For DM subjects monitored with POC-FSBG and CGM (**Intervention Group**) or with POC-FSBG only (**Control Group**): In both groups, participants will have their glucose values monitored with POC-FSBG as follows: Pre-breakfast (fasting), pre-lunch, pre-dinner, at bedtime and at 3am) [6, 36]. For admitted veterans that are not eating or that receive continuous enteral nutrition, we will check POC-FSBG every 6 hours [15].

For DM subjects enrolled in the POC-FSBG and CGM (**Intervention Group**), in addition to POC-FSBG, glucose values will be monitored continuously, over 24 hours, by CGM.

POC-FSBG will be measured any time the CGM alarms. In addition POC-FSBG will be measured any time a participant (in either group) develops symptoms that are suggestive of hypoglycemia.

Insulin Treatment:

Titration of insulin will be not made based on the CGM values. Titration adjustments of the insulin regimen will be made by the inpatient diabetes management service team, based on POC-FSBG values. Titration of basal insulin (glargine) will be made based on the fasting am glucose values, based on the following algorithm (**Table 1**).

Table 1. Titration of basal insulin (glargine) [35]			
Fasting am BG values	Basal dose (IGIa) adjustments		
If BG< 60 mg/dl	Decrease dose by 20%		
If BG 60-79 mg/dl	Decrease dose by 10%		
If BG 80-139 mg/dl	No change		
If BG 140-179 mg/dl	Increase dose by 10%		
If BG 180-249 mg/dl	Increase dose by 20%		
If BG >250 mg/dl	Increase dose by 30%		

Titration of correctional (sliding scale) insulin will be adjusted daily based on fasting and pre-meals capillary BG levels (**Table 2**) [35]. If subjects are placed NPO, capillary blood glucose values will be checked every 6 hours and insulin will be administered based on the same insulin algorithm (**Table 2**). Subjects will be treated initially with the "insulin sensitive" regimen, as this group of individuals has a high risk for hypoglycemia. If capillary BG is persistently above 140 mg/dl throughout the day in the absence of hypoglycemia, we will increase the insulin scale regimen from the "insulin sensitive" to the usual or from the "usual" to the "insulin resistant" regimen [15, 35]. If a research subject has POC-FSBG <80 mg/dl, we will decrease accordingly the insulin scale regimen from "insulin resistant" to "usual" or from "usual" to "insulin sensitive" [15, 35].

Table 2. Titration of Correctional (Sliding Scale) Insulin (Novolog) [35].			
BG Values	Insulin sensitive	Usual	Insulin resistant
<80 mg/dl	-1	-1	-2
80-139 mg/dl	0	0	0
140-159 mg/dl	0	+1	+1
160-199 mg/dl	+1	+1	+2
200-249 mg/dl	+2	+3	+4
250-299 mg/dl	+3	+5	+7
300-349 mg/dl	+4	+7	+10
>350 mg/dl	+5	+8	+12

Titration of short acting prandial insulin will be based on pre-lunch, pre-dinner and bedtime BG, adjusting the previous administrated prandial insulin dose, targeting BG values 140-180 mg/dl. If BG is 181-250 mg/dl we will increase the prandial dose by 15%, if it is 251-300 by 20% and if BG was greater than 300 mg/dl we will increase by 30%.

GGM alarm settings and Prevention of Hypoglycemia:

CGM alarms will be set to <85 mg/dl (for prevention for low blood glucose levels) and >400 mg/dl (for alarming for high blood glucose levels). If CGM alarms for low glucose values, a POC-FSBG will be obtained. If it is the POC-FSBG is between 70-85 mg/dl, at least 10 gr of carbohydrates will be given to the subject as a preventive measurement for hypoglycemia. An additional POC-FSBG will be obtained in 15 min in order to confirm that the BG are rising. Similarly, the group of patients that are managed by POC-FSBG only **(Control Group),** if a POC-FSBG will be found to be between 70-85 mg/dl, at least 10 gr of carbohydrates will be given to the subject as a preventive measurement.

Treatment of Hypoglycemia

Treatment of hypoglycemia will be similar in the 2 groups and will be based on standard hospital protocols.

Outcome Measures

Aim 1: Hypoglycemic values will be defined as POC-FSBG<70 mg/dl and will be classified as severe if it involved loss of consciousness and/or seizures [35] We will evaluate if there is a difference in the total number of hypoglycemic events between the 2 groups, by evaluating POC BG values. Time spent during hypoglycemia will be also calculated in both groups, using data from GCM devises.

Aim 2: We will compare time spent in hyperglycemia (>180 mg/dl) between the 2 groups. We will compare glucose values obtained from the CGM devises from Interventional group (unblinded) and Control group (blinded).

Aim 3: We will compare time spent in severe hyperglycemia (>300 mg/dl) between the 2 groups. We will compare glucose values obtained from the CGM devises from Interventional group (un-blinded) and Control group (blinded).

Statistical plan

Descriptive statistics including means and SDs will be computed for continuous variables, and counts and proportions will be computed for categorical variables. Wilcoxon's rank sum test will be applied to comparing continuous variables between the intervention group and the standard-of-care group. Fisher's exact test will be used to compare categorical variables between the two groups. Data analysis will be carried out using SAS statistical program.

Safety

All subjects that participate in the proposed study will be patients with DM that will be admitted to the VABMC hospital for medical reasons. Glucose monitoring for **Control group** will be made with POC-FSBG testing that represents standard of care. **Interventional group** will be monitored as above, however additionally CGM will be utilized. To address any daytime or overnight problems the PI will be on call. The PI is well versed in trouble shooting problems with the CGM devices. Nurses and house staff will receive additional training for the CGM devices.

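### Aim 1 counts hypoglycemic events from POC readings, but alarm-triggered POC tests exist only in the Intervention arm, so the count is biased against the intervention

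*Combined protocol and SAP*

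**What the plan says.** Under B. Aims, Aim 1 is to determine whether the trial can "prevent more hypoglycemic values/ events in the Intervention Group vs Control group", and Hypothesis 1 repeats the same pairing of values and events. Outcome Measures, Aim 1, defines only the value: "Hypoglycemic values will be defined as POC-FSBG<70 mg/dl". It then evaluates whether there is a "difference in the total number of hypoglycemic events between the 2 groups, by evaluating POC BG values". No rule says when an event starts or ends, or how several low readings are combined. CGM time in hypoglycemia is calculated as well, without a restated threshold.

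The sources of POC readings are as follows:

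- **Scheduled, both arms** (Lab Values and Glucose Measurements): "Pre-breakfast (fasting), pre-lunch, pre-dinner, at bedtime and at 3am", or every 6 hours for patients who are not eating or are on continuous enteral nutrition.
- **Symptom-triggered, both arms** (same section).
- **Alarm-triggered** (same section): "POC-FSBG will be measured any time the CGM alarms". The low alarm is set at <85 mg/dl. For Control, B. Aims (Groups) states that "CGM results will be blinded (for both the investigators and the subjects", so this route can operate only in the Intervention arm.
- **Recheck** (alarm settings and prevention section): after an alarm and a POC of 70-85 mg/dl, "An additional POC-FSBG will be obtained in 15 min in order to confirm that the BG are rising". The parallel Control sentence repeats the carbohydrate step and does not mention a recheck.

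Once a patient is hypoglycemic, treatment is described as similar in the two groups under standard hospital protocols. No retest rule is given.

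**The concern.** An event count obtained by testing depends on how often, and when, one tests. Here one arm has an additional testing route that fires when glucose is falling, at a threshold above the 70 mg/dl outcome cut-off. Lows that go unrecorded in Control between scheduled tests will tend to be recorded in the Intervention arm. The treatment being evaluated therefore changes both the true number of lows and the chance that each is counted, and the two effects push the count in opposite directions. A real reduction could look smaller, vanish or reverse. The Background says this pilot is meant to supply preliminary data for larger studies, so a distorted event ratio would carry into their planning.

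The missing event definition is a second, separate problem: the same low may be counted once or several times, depending on who does the counting.

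**Working it through.** The plan states no event rate, effect size or sample size, so there is no figure to reproduce. The check is an illustration with equal true lows in both arms.

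**Inputs from the documents**

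- 5 scheduled tests per day.
- Alarm tests in the Intervention arm only.
- 26.3% of hypoglycemic events asymptomatic in the inpatient CGM study cited in the Background. This caps the symptomatic share at 1 - 0.263 = 0.737.

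**Assumptions, not in the documents**

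- Episode length below 70 mg/dl: D = 30, 60 or 120 min, falling evenly over the day.
- Chance of a symptom-triggered test during the episode: s = 0, 0.3 or 0.737.
- Chance that an alarm-triggered test reads <70: a = 0.5 or 0.9.
- The detection routes act independently.

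**Formulas**

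- Scheduled test falls within the episode: h = 5 × D / 1440, giving 0.104, 0.208 and 0.417.
- Detection in Control: 1 - (1 - h)(1 - s).
- Detection in Intervention: 1 - (1 - h)(1 - s)(1 - a).

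**Worked case: D = 60, s = 0.3, a = 0.9**

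- Control: 1 - 0.792 × 0.7 = 0.446, or 45 per 100 true episodes.
- Intervention: 1 - 0.792 × 0.7 × 0.1 = 0.945, or 94 per 100.
- Ratio: 2.12, with no difference in true lows.

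**Range over D and a.** The last column multiplies by 0.70, an assumed true 30% reduction.

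| s | Detected-episode ratio, no true effect | Apparent ratio if the true ratio is 0.70 |
|---|---|---|
| 0 | 1.700 to 8.740 | 1.19 to 6.12 |
| 0.3 | 1.345 to 2.513 | 0.94 to 1.76 |
| 0.737 | 1.091 to 1.277 | 0.76 to 0.89 |

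A detection ratio of 1 / 0.70 = 1.43 is enough to hide a 30% reduction completely.

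**Does merging repeat readings repair this?** Let q be the chance that a retest of a low is still <70, so that a detected episode yields 1 / (1 - q) low readings. With q = 0.5 (assumed) and the same retesting in both arms, the worked case gives 89 low readings in Control and 189 in Intervention, a ratio of 2.12. Counted once per episode, it gives 45 and 94, again 2.12. The repeats cancel and the detection gap remains. Restricting the count to scheduled readings makes detection equal to h in both arms, so the ratio is 1 when true lows are equal. Counting from CGM in both arms likewise removes the alarm-driven difference.

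**The case against.** A reader might infer more: that every POC reading <70 is an event, that the 15-minute recheck makes the Intervention arm count the same low twice, and that repeats therefore drive the bias. The documents do not support this, for three reasons.

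- No sentence makes each reading an event. The event is simply undefined.
- The recheck follows a POC of 70-85 mg/dl. If the recheck is below 70, it is the first low reading of that episode. It adds a detection, not a repeat.
- Most repeats would come from follow-up after a reading <70, and treatment at that stage is described as similar in both groups.

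If repeats occurred at a rate q = 0.2 to 0.6 in the Intervention arm and never in Control, a true ratio of 0.70 would appear as 0.70 × (1 + q), or 0.84 to 1.12. With equal repeats, 0.70 × (1 + q) / (1 + q) = 0.70. Nothing shows that Control lows go unretested, so those figures should not be used. Because no retest rule is given, unequal repeats cannot be excluded either.

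It can also be said that this is a pilot, that the bias would not create a false claim of benefit, and that CGM time in hypoglycemia is unaffected by POC frequency. All three hold and limit the seriousness of the point. They do not rescue the POC event count, which remains a stated Aim 1 comparison.

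**Conclusion.** The point stands on the text: the Aim 1 POC event count rests on testing that is unequal by design, and the inequality runs against the intervention. Its size is unknown. With equal true lows, the illustrated detection ratios run from 1.09 to 8.74. They are smallest when most lows prompt a test through symptoms, and largest when lows are short and silent. All depend on the assumed D, s and a. Over much of that range a true 30% reduction would be hidden or reversed; at s = 0.737 it would only be diluted.

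The lack of an event definition is also real and allows one episode to be counted more than once, but it is a separate ambiguity with no demonstrated direction between arms. The two alarm-section sentences leave open whether the recheck applies to Control. That is an ambiguity rather than a contradiction. The point should be fixed, but it does not undermine the trial as a whole.

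**What to change.** 1. **Comparison on equal terms.** Base the between-arm POC comparison on scheduled readings only, identified by protocol time point. Alternatively, count events from the CGM data collected in both arms, at the same <70 mg/dl threshold. Symptom-triggered readings should not enter the main comparison, although both arms have them: in the Intervention arm an alarm can prompt the test before symptoms appear, so such lows would be classed as alarm-triggered there and as symptom-triggered in Control.
2. **Separate reporting.** Report alarm-triggered, symptom-triggered and recheck readings by arm, outside that comparison.
3. **Event definition.** Distinguish a value from an event. Count each episode once, by the same rule in both arms, with a start, an end and a fixed time separation. The separation matters: merging all consecutive low readings would join distinct lows at separate scheduled times, such as bedtime and 3 am, in the less-tested arm.
4. **Reconcile the text.** The alarm-section sentences must be reconciled on whether the 15-minute recheck applies to both groups.

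Cost: fewer POC events are counted, so that comparison is less precise. Scheduled readings and CGM data are already collected. The plan does not say that the reason for each POC test is recorded, so reporting by trigger requires recording it for unscheduled tests.

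### Table 1 raises glargine on the fasting value alone, so a treated overnight low can be followed by a basal increase in either arm

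*Combined protocol and SAP*

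**What the plan says.** Section C, Insulin Treatment, puts dosing in the hands of a specialist service: "Titration adjustments of the insulin regimen will be made by the inpatient diabetes management service team, based on POC-FSBG values". For the long-acting insulin it then narrows the input: "Titration of basal insulin (glargine) will be made based on the fasting am glucose values, based on the following algorithm". Table 1 has six rows, all keyed to the fasting value: −20% below 60 mg/dl, −10% at 60–79, no change at 80–139, +10% at 140–179, +20% at 180–249 and +30% above 250. None of the three increase rows mentions hypoglycemia.

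The correctional (sliding-scale) insulin in the same section has a condition on going up, "If capillary BG is persistently above 140 mg/dl throughout the day in the absence of hypoglycemia, we will increase the insulin scale regimen", and a trigger for going down, "If a research subject has POC-FSBG <80 mg/dl, we will decrease accordingly the insulin scale regimen". Participants start on the lowest scale, "as this group of individuals has a high risk for hypoglycemia".

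Lab Values and Glucose Measurements schedules POC checks in both arms: "Pre-breakfast (fasting), pre-lunch, pre-dinner, at bedtime and at 3am". It adds: "In addition POC-FSBG will be measured any time a participant (in either group) develops symptoms that are suggestive of hypoglycemia". Under Outcome Measures, Aim 1, "Hypoglycemic values will be defined as POC-FSBG<70 mg/dl". The section on treating hypoglycemia refers to the hospital's usual protocols and says nothing about the next basal dose.

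**The concern.** The protocol collects POC readings at bedtime, at 3am and on symptoms, but none of them is an input to Table 1. A participant can be treated for a low in the night, wake with a raised fasting value, and be assigned more glargine that morning. The same low blocks a step-up of the correctional scale and calls for a step-down, so the two parts of one insulin regimen respond differently to one event.

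Enrolment requires a risk factor for hypoglycemia or a recent significant episode in hospital, so these are patients in whom an unneeded rise in long-acting insulin matters. A POC reading below 70 mg/dl is also the Aim 1 event, so the dosing rule could add to the outcome that the trial sets out to prevent.

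**Working it through.** The plan states no figure on this point. The check is a trace of the written rules, followed by dose arithmetic on labelled assumptions.

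**Step 1: trace a POC reading below 70 mg/dl through both rules.** Inputs are Table 1 and the correctional-scale text in Insulin Treatment.

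| When the low occurs | Next fasting value (mg/dl) | Correctional scale | Glargine under Table 1 |
|---|---|---|---|
| At the fasting check, below 60 | – | step down | −20% |
| At the fasting check, 60–69 | – | step down | −10% |
| Any other check | 80–139 | step down | no change |
| Any other check | 140–179 | step down | +10% |
| Any other check | 180–249 | step down | +20% |
| Any other check | above 250 | step down | +30% |

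The gap is therefore confined to lows outside the fasting check that are followed by a fasting value of 140 or more. The step-down does not fill it. It changes the correctional scale only, and a participant still on the starting scale has no lower one to move to.

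**Step 2: how far glucose must rise to reach each increase row.** The highest whole-number reading that counts as hypoglycemia is 69 mg/dl.

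- +10% row: 140 − 69 = 71 mg/dl
- +20% row: 180 − 69 = 111 mg/dl
- +30% row (first whole number above 250): 251 − 69 = 182 mg/dl

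These are minimum rises; a deeper low needs more. After a 3am low, the rise must also happen between 3am and the fasting check. The +10% row is the easiest to reach.

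**Step 3: size of the increase compared with holding the dose.** Excess = p × T × W × f, where p is the Table 1 step, T the total insulin dose (u/kg/day), W the weight (kg) and f the basal share. The documents give no doses or weights. Their one anchor is the inclusion criterion of insulin use above 0.6 u/kg, read here as a daily dose. That criterion is one of several alternatives, so some participants may take less than 0.6. It has no upper limit, so others will take more. The last line doubles 0.6 to show the effect.

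| Assumed T × W × f | Basal dose | +10% | +20% | +30% |
|---|---|---|---|---|
| 0.3 × 60 × 0.4 | 7.2 u | 0.7 u | 1.4 u | 2.2 u |
| 0.6 × 80 × 0.5 | 24 u | 2.4 u | 4.8 u | 7.2 u |
| 0.6 × 100 × 0.6 | 36 u | 3.6 u | 7.2 u | 10.8 u |
| 1.2 × 100 × 0.6 | 72 u | 7.2 u | 14.4 u | 21.6 u |

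**Step 4: frequency.** The documents give no rate of non-fasting lows followed by a fasting value of 140 or more, so no expected number of such increases can be computed.

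**The case against.** The strongest reply is that a diabetes service applies Table 1, with every POC value in front of it, and would not raise glargine the morning after a low. That is plausible and limits the practical risk. It does not close the gap: the sentence after the one naming the team ties glargine to the fasting value, and nothing written tells the team to withhold an increase. The hospital's hypoglycemia protocols, or the publication cited for Table 1, might contain such a rule. Their content is not in the documents, and the protocol invokes the former only for treating the low.

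A second reply is that the contrast with the correctional scale is weak, since a day spent persistently above 140 mg/dl leaves little room for a reading below 70. This partly stands: the clause is thin evidence of a deliberate safeguard that was left out of Table 1. The point rests on what Table 1 does, not on that contrast.

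A third is that a hold after any low would be too broad. A low before lunch or dinner may reflect prandial insulin or a missed meal, and blocking a basal increase at a fasting value above 250 would work against Aims 2 and 3. This stands, and is why the automatic hold should cover overnight lows only.

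A fourth is that alarm-prompted checks occur only in the Intervention arm, so a POC-triggered hold lets CGM steer basal insulin indirectly. This also stands as a possibility. The trigger is still a POC value, which respects the rule against titrating on CGM, but nothing in the documents shows that the resulting difference between arms would be small.

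The protocol's other safeguards also help: carbohydrate at POC 70–85 in both arms, the CGM alarm below 85 in the Intervention arm, and the basal cut when the fasting value itself is below 80. None addresses a low that is followed by a high fasting value.

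**Conclusion.** The point holds as a gap in a written dosing rule. Followed literally, Table 1 can raise glargine after a documented, treated low in patients selected for hypoglycemia risk. The most plausible step is +10%: 2.4 u on the assumed 24 u, and 0.7 to 7.2 u across the assumptions shown. Confidence is high about the text. The clinical consequence is not quantified, because the frequency is unknown and the team may depart from the table.

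A reader might infer three stronger things that the documents do not support:

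- **Bias between the arms.** The same table applies to both, and basal dosing uses one scheduled value collected alike in each.
- **Increases of 30% as a typical result.** That row needs a rise of at least 182 mg/dl.
- **Increases after lows as a certainty.** The specialist service can withhold them.

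The prandial increases of 15%, 20% and 30% also carry no stated hypoglycemia condition, but they are not assessed here.

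**What to change.** Add to Table 1, identically for both arms: *No basal increase if any POC-FSBG from bedtime to the fasting check was below 70 mg/dl. After a daytime POC-FSBG below 70 mg/dl, the diabetes team reviews whether prandial or basal insulin was responsible before any basal increase. Decrease rows unchanged.* For participants on six-hourly checks, name the readings that count as overnight.

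Do not use CGM values as the trigger, since the protocol excludes them from titration. Do not use carbohydrate given at POC 70–85 either, since that range is not hypoglycemia under Aim 1. Tabulate holds by arm and by what prompted the reading (scheduled check, symptoms or CGM alarm). This would show any imbalance but would not remove it.

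The cost is a minor amendment that uses readings already taken for care. The downsides are slightly slower basal up-titration, with some added hyperglycemia in the participants affected, and possibly more holds in the Intervention arm through alarm-prompted checks, of unknown size.

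### Aim 1 counts POC readings <70 mg/dl, but alarm-triggered POC tests occur only in the Intervention Group, so the count most likely understates any benefit

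*Combined protocol and SAP*

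**What the plan says.** Section B sets Aim 1: "To determine if we can prevent more hypoglycemic values/ events in the Intervention Group vs Control group". Outcome Measures, Aim 1 defines a hypoglycemic value as a POC-FSBG reading <70 mg/dl and then states: "We will evaluate if there is a difference in the total number of hypoglycemic events between the 2 groups, by evaluating POC BG values". The same paragraph adds CGM time in hypoglycemia for both groups.

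POC readings arise in four ways:

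- **Scheduled, both arms** (Lab Values and Glucose Measurements): "Pre-breakfast (fasting), pre-lunch, pre-dinner, at bedtime and at 3am", so five a day. For patients who are not eating or are on continuous enteral feeding, "we will check POC-FSBG every 6 hours".
- **Symptoms, both arms** (same section): "POC-FSBG will be measured any time a participant (in either group) develops symptoms that are suggestive of hypoglycemia".
- **CGM alarm** (same section): "POC-FSBG will be measured any time the CGM alarms". The alarm section sets the low alarm at <85 mg/dl.
- **15-minute recheck** (alarm section): written for a reading of 70-85 mg/dl after an alarm, when carbohydrate is given. The sentence on the Control Group repeats the carbohydrate but not the recheck.

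For the Control Group, Section B says "CGM results will be blinded", to investigators and subjects alike. The Statistical plan names Wilcoxon and Fisher tests. It makes no adjustment for the number of POC tests or the length of monitoring.

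**The concern.** The intervention adds tests for its own outcome event, in one arm only. An asymptomatic low in the Control Group is counted only if a scheduled test happens to meet it. The same low in the Intervention Group may also be found through the alarm. Nothing excludes alarm or recheck readings from the count, and nothing merges several low readings into one event. Aim 1 itself treats values and events as interchangeable.

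The Background reports that CGM detects more lows than POC testing and presents prevention as the next question. A count that rises with detection cannot cleanly answer a question about prevention. A real reduction would probably look smaller than it is, and a modest one could look absent. The pilot is also meant to inform larger studies, so an attenuated effect could carry into their design.

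**Working it through.** The documents give no sample size, event rate or effect size, so there is no stated figure to reproduce and no power statement to make. The check is a simple detection model.

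**Inputs from the documents.** Five scheduled tests a day (Lab Values and Glucose Measurements). Asymptomatic share A = 0.263 (Background; a cited study in insulin-naive patients, denominator not shown).

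**Assumptions.** Lows last L = 30, 60 or 120 minutes and fall evenly over the day. Every symptomatic low is tested, as the protocol requires. Alarm tests find a share a of the lows otherwise missed. The true reduction is p.

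**Formulas.**

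- Chance that a scheduled test meets a low: q = 5L/1440.
- Control detection: dC = (1 − A) + A·q.
- Intervention detection: dI = dC + a(1 − dC).
- Observed ratio of counts: (1 − p)·dI/dC.

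For L = 60: q = 300/1440 = 0.208; dC = 0.737 + 0.263 × 0.208 = 0.792; with a = 1 and p = 50%, the ratio is 0.50 × 1/0.792 = 0.63.

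| | L = 30 | L = 60 | L = 120 |
|---|---|---|---|
| q | 0.104 | 0.208 | 0.417 |
| dC | 0.764 | 0.792 | 0.847 |
| True ratio 0.50, a = 1 | 0.65 | 0.63 | 0.59 |
| True ratio 0.50, a = 0.5 | 0.58 | 0.57 | 0.55 |
| True ratio 0.80, a = 1 | 1.05 | 1.01 | 0.94 |
| True ratio 0.80, a = 0.5 | 0.92 | 0.90 | 0.87 |

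With four tests a day, dC is 0.759, 0.781 and 0.825, which changes little.

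**Sensitivity to Control detection.** With A = 0.50 (assumed), dC is 0.552, 0.604 and 0.708, and a true 0.50 with full capture appears as 0.91, 0.83 and 0.71. For a true 0.50 to look reversed, dI must exceed 2·dC, which is possible only if dC < 0.50. With A = 0.263, that means the share of symptomatic lows actually tested is below (0.5 − q)/(0.737(1 − q)) = 0.60, 0.50 or 0.19. The same background study's 12 versus 55 events, read as dC = 12/55 = 0.218, would make a true 0.50 appear as 0.95 (a = 0.25) to 2.29 (a = 1). That reading is uncertain and is not a bound.

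**Direction.** Suppose action after alarms shortens lows, so that scheduled and symptom tests in the Intervention Group detect only k·dC. Then dI = k·dC + a(1 − k·dC), and dI > dC requires a > dC(1 − k)/(1 − k·dC). For k = 0.9 this is 0.245, 0.276 and 0.356; for k = 0.8 it is 0.393, 0.432 and 0.525. Above these values the bias runs against the intervention; below them it runs in its favor.

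**The case against.** The strongest reply is that Aim 1 already includes CGM time in hypoglycemia in both arms, which does not depend on how often POC tests are done. That stands as a real mitigation. It does not repair the event count, and the plan does not say which measure answers Aim 1 if the two disagree. A cut-off of <70 mg/dl for the CGM measure is the natural reading, but the definition names POC-FSBG only, whereas Aims 2 and 3 state their CGM cut-offs.

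The size is also open to challenge. The two background figures imply very different Control detection (about 0.8 against 0.218), lows may cluster near test times, which would shrink the bias, and the model counts each low once, so it leaves out repeat readings. All of this stands: the figures are illustrations.

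The direction is likely, not certain. With a 10% loss of background detection, alarms catching 25% of the remaining lows fall short of the threshold for two of the three durations. Fewer lows because of preventive carbohydrate, however, are a true treatment effect and not an artifact.

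Two smaller points. The recheck may have been meant for both arms, since the Control sentence is introduced as a parallel; the alarm tests alone still create the imbalance. No sentence says that Control alarms are silent, but an alarm that prompted a test there would break the blind.

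**Conclusion.** The concern holds. Followed exactly, the plan produces an Aim 1 event count with unequal ascertainment between arms. That testing is unequal is clear from the text; that the result understates benefit is likely; the amount is unknown. Under the base assumptions (26.3% asymptomatic, all symptomatic lows tested, lows of 30 to 120 minutes) a halving of lows is attenuated to a ratio of 0.55 to 0.65 at half to full alarm capture. At full capture a 20% reduction ranges from barely visible to absent (0.94 to 1.05). Reversal of a true halving needs Control detection below 0.50 and Intervention detection more than twice that. The planned CGM time measure limits the harm but has no declared priority. This should be fixed.

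**What to change.** Base the main Aim 1 comparison on CGM data in both arms, as Aims 2 and 3 already are.

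- **Main measure:** time <70 mg/dl as a share of each patient's sensor wear time, compared by the planned Wilcoxon test.
- **Second measure:** distinct CGM episodes <70 mg/dl per day of wear, under one pre-specified rule for both arms (for example, at least three consecutive 5-minute readings, a proposed convention), also compared by Wilcoxon.
- **Supportive POC measure:** record what triggered each POC reading (scheduled, symptom, alarm, recheck). Count lows at scheduled times only, merge repeats by a stated rule (for example, lows within 2 hours of the first count once, also a proposed convention), and express them per monitored day. Add symptom-triggered readings as a sensitivity analysis, and report alarm and recheck readings descriptively.
- **Severe events:** report them in both arms whatever triggered the test.

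The cost is outcome and SAP wording plus a trigger code on each POC reading; sensors are already worn in both arms. No alarm setting or clinical management changes. Three drawbacks should be stated:

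1. Sensor error and wear gaps (such as removal for MRI or CT) enter the main measure, and the wear-time denominator handles gaps only in part.
2. Scheduled-only POC counts can be biased the other way if alarms shorten lows. With lows cut from 60 to 45 minutes, a true 0.50 would appear as 0.50 × 45/60 = 0.38. They are a check, not an unbiased estimate.
3. Unblinded patients may report symptoms differently, which affects the symptom-triggered sensitivity analysis.
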